## **Comparative Effectiveness of Two Self-Assessment Tools: KIOS-Bipolar or eMoods: A Randomized, Open 52 Week Study for Persons with Bipolar Disorder**

**[name], [name], [name], [name], [name], [name].**

### **Abstract/Project Summary**

#### **A. Objective: *What we propose to do***

Bipolar disorder (BD) is a complex chronic illness characterized by recurrent, often dramatic mood changes. Self-management of BD is an important component of treatment, but is likewise complex and can be fraught with difficulties, including misunderstanding of the condition and a lack of self-awareness. Combined with the nationwide shortage of mental healthcare providers and the advent of the Affordable Healthcare Act, patients are assuming an increased role in understanding and managing their chronic conditions. At the same time, the emergence of mobile health and computational tools are engaging patients in self-management by enabling timely access to information and resources.

The goal of this project is to complete the development of a patient-centered software system and mobile app to assist in managing bipolar disorder. In Phase I, we developed a novel computational tool known as KIOS-Bipolar. Based on concepts from nonlinear systems (chaos) theory, KIOS-Bipolar tracks multiple interacting symptoms to determine the precise state of a BD patient. Once the patient's state is identified and the trajectory of the patient is established, KIOS-Bipolar produces advice specific to the patient's condition to help manage the course of the disease. To facilitate user convenience for the software, KIOS-Bipolar was converted to an online tool with mobile access. Twenty bipolar patients evaluated KIOS-Bipolar in a twelve week field trial. No technical problems with the software were observed and results showed that patients had significantly more reductions in symptom severity than increases. The development of this innovative tool to help patients self-manage BD has the potential to profoundly impact public health and achieve significant commercial success.

This Phase II study has the specific aim of evaluation of KIOS-Bipolar in a randomized, open 52 week effectiveness study of 120 bipolar subjects in current treatment at three socioeconomically diverse academic health science centers. Concurrent with this clinical effectiveness study, the research team, funded by the same NIH grant, will refine prototype software and integrate data security and establish quality standards into the KIOS-Bipolar system.

#### **The clinical trial will:**

- a. Assess aggregate time spent in seven primary clinical states of BD (remitted; subsyndromal depression, mania or mixed state; and syndromal depression, mania or mixed state).
- b. Assess the weekly completion of KIOS-Bipolar and eMoods.
- c. Determine indices of patient satisfaction with the format, ease of use, time required and patient motivation for continuing use of the patient tools both during the trial and following completion.
- d. Determine patient satisfaction with the clinical information on BD illness trajectory and recommendations to facilitate good health and effective interventions. Note that eMoods does not provide this element of information, therefore no comparative data will be feasible for this one objective.
- e. Assess patient scored life function indices (Life Function Questionnaire (LFQ) over the 52 week period of the study.
- f. Assess the relationship between the 8 symptom items in K-B with relevant items rated both by clinicians and as self-assessments by patients at seven time points (week 0, 8, 16, 24, 32, 40 and 52) in the study. These are times at which clinical care visits will routinely occur, and therefore will not add either to extra burden on the participants, or extra contact time with staff. Subjects randomized to eMoods will be similarly scheduled, with the correlations limited to those feasible with the eMoods product. Self-assessments with the 27 item BISS-Self are routinely obtained as part of regular treatment visits.

**Table 1. Schema for Randomized Clinical Trial**

Week	0	1-7	8	9-15	16	17-51	24, 32, 40	52	RS
MINI-6.0, Demographics/course of illness	X								
K-TABS/eMoods	X	X	X	X	X	X		X	
Life Functioning Questionnaire	X		X		X			X	
BISS-42,	X		X		X		X	X	
BISS Self-Assessment	X		X		X		X	X	X
KIOS NIH Software Evaluation Form					X			X	

The clinician administered scale will be the 42 item Bipolar Inventory of Symptoms Scale (BISS), however comparisons will be limited to the symptom areas represented in both K-B and eMoods, e.g., depression and mania subscales; depression, mania, irritability and anxiety domains. The BISS Self (BISS-S) is a 27item scale covering similar symptoms to the BISS, but answered as yes/no, rather than the 0-4 range of the BISS. The MINI is a structured diagnostic interview providing current and lifetime psychiatric diagnoses, requiring approximately 20 minutes.

g. Estimate the utility of ancillary features of Kios-Bipolar or eMoods. These features include capability to submit to the investigative staff displays of symptom trajectories for the patient's medical record and visual displays of selected aspects of the patient's illness/wellness. No transmission of data to treating clinical staff will occur as component of this study.

h. Assess sensitivity of K-B assessed improvement or worsening by comparison with assessment by BISS-Self and BISS-42.

**B. Sample Size and Enrollment:**

One hundred twenty (120) participants, 50 at UTHSCSA site, and 35 each at The University of Louisville Research Foundation, Inc. and The University of Cincinnati, will be involved in the clinical trial in Aim 2. All study participants will sign informed consent forms prior to being enrolled and will be recruited from the UTHSCSA, the University of Louisville or the University of Cincinnati.

**Inclusion Criteria:**

1. Male or female outpatients 18 years of age or older
2. Bipolar I or II disorder as assessed by MINI 6.0
3. In psychiatric outpatient treatment at UTHSCSA, University of Louisville, or Lindner Center of Hope, Mason Ohio
4. Currently taking mood stabilizer or second generation antipsychotic for 4 weeks or longer
5. Ability to access Kios-Bipolar or eMoods (via computer, smartphone or tablet)

**Exclusion Criteria:**

1. Unwilling or unable to comply with study requirements
2. Drug/alcohol dependence within the past 30 days

**Early termination:**

Participation in the study will be terminated if a patient has a score of 4 on the BISS suicide item, BISS-Depression Scale  $\geq 50$ , or BISS Mania Scale  $\geq 35$  for 4 consecutive weeks, or if the treating psychiatrist determines that a patient poses an imminent risk of self-harm.

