**Table 2. BISS Item and Corresponding KIOS-BIPOLAR Questionnaire**

BISS Item	KIOS-BIPOLAR Question
Affective Lability	Have your emotions shifted fairly suddenly at times?
Sadness	Have you felt depressed, sad or down?
Irritability	Have you felt easily irritated, angry or resentful?
Pessimism	Have you been discouraged, pessimistic or felt hopeless?
Anxiousness	Have you felt tense or anxious?
Less Need for Sleep	Were there nights you needed less sleep than usual?
Psychomotor Slowing	Have you felt slowed down?
Energetic	Have you had more energy than usual to do things?

**Software:** Subjects assigned to KIOS-Bipolar will have the app loaded onto their preferred device. The program is available for iPhone and Android devices, and accessible on a pc. The research coordinator will demonstrate the KIOS-Bipolar operation with the subject and ask the subject if he/she has any questions about the procedures of the trial. A phone number and email address will be provided to allow the subject to make contact if any question arises after leaving the clinic. The data entry procedure will take less than 5 minutes per session, with most subjects completing their entries in 2 minutes.

For participants who have been randomized to the eMoods App an additional procedure will occur. After each completed weekly entry on eMoods, the participant will have the option to email the results to the Research Coordinator weekly or postpone sending data until their scheduled research visit.

The subject will be told that an email, text, or push notification reminder will be sent one day after a missed scheduled assessment. The participants phone number will be shared with a third-party (Twilio) solely for the purpose of reminding the participant to complete their questionnaire. This information will only be used for the administration of the push notification and will be kept strictly confidential. The participant will not have the option to opt out of the notification. For participants randomized to KIOS-Bipolar, a text message reminder will be sent one day after a missed scheduled assessment. The participant's phone number will be added to New Patient section in KIOS-Bipolar.

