## RISKS TO HUMAN SUBJECTS

### ***a. Human Subjects Involvement, Characteristics, and Design***

The collaborating sites are the UTHSCSA, the University of Louisville and the University of Cincinnati. Under the direction of [name], Biomedical Development Corporation will create an identical set of study binders containing source documents and case report forms for each of the study sites. Each site will have a designated study coordinator who will be responsible for obtaining, managing and protecting the data. All study materials will be kept under lock and key. The study sites will be monitored throughout the project period by BDC for study compliance, including a preliminary monitoring visit prior to the initiation of the trial to ensure that the study site is adequately equipped and staffed to perform the trial.

The Federal Wide Assurance number for the UTHSCSA is FWA00005928. The Assurance of Compliance number for the UTHSCSA is IRB00000553. The Federal Wide Assurance number for the University of Louisville is FWA00002211. The Federal Wide Assurance number for the University of Cincinnati is 00003152. The Federal Wide Assurance number for Biomedical Development Corporation is FWA0000749.

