### ***c. Potential Risks***

- There are only minimal risks associated with participation in this study. There is no intervention component in the trial. None of the planned activities are likely to be stressful to the subjects. However, it is possible that a subject could worsen in a time frame between clinic treatment visits. We will convey the evidence of the person's worsening to his/her psychiatrist or other therapist.

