### ***e. Protections Against Risk***

Minimal risk to subjects or subject's privacy is anticipated. Nonetheless, we recognize the need for strict protection of confidentiality in this study. To address this, records of patients will be retained as required by statute in locked files. All computer files will be password protected. Subjects will be identified in common-use computer files by ID number only. Research reports and publications will report only group data and not individual names. Identities of subjects will not be revealed in the publication or presentation of any results from this project. All investigators and research staff at the respective institutions have completed the requirements for human research subjects' protection. All investigators and research staff at BDC have completed the requirements for human subjects' protection. The study will be performed in accordance with HIPPA regulations and approved by the IRBs at the UTHSCSA, the University of Louisville and the University of Cincinnati.

Participation in the study will be terminated if a patient has a score of 4 on the BISS suicide item, BISS Depression Scale  $\geq 50$ , or BISS Mania Scale  $\geq 35$ , or if the treating psychiatrist determines that a patient poses an imminent risk of self-harm.

All subjects enrolled in the trial will have been under care of a psychiatrist at their respective institutions prior to enrolling in the study. All subjects will continue to receive evidence-based care provided by outstanding psychiatrists at the three sites. Participation in the study will not impact the patient's routine clinical care for his/her bipolar condition. The study's planned visits will generally be scheduled to coincide with the patient's regularly scheduled clinic visits both for convenience and in order to not interfere with regular care.

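### The two statements of the early-termination rule differ on a four-week duration (certainly for mania), and the BISS schedule cannot establish that duration

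*Combined protocol and SAP*

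**What the plan says.** The rule appears twice, both times as current text.

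- **Early termination** lists three BISS limits (suicide item at 4, Depression at 50 or more, Mania at 35 or more). Directly after the mania limit it continues: "for 4 consecutive weeks, or if the treating psychiatrist determines that a patient poses an imminent risk of self-harm".
- **e. Protections Against Risk** begins "Participation in the study will be terminated if a patient has a score of 4 on the BISS suicide item, BISS Depression Scale" and goes on with the same depression and mania cut-offs and the same psychiatrist clause. It has no duration.

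Nothing says which statement governs.

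The limits are on the clinician-rated BISS. Item f under The clinical trial will places the clinician ratings and the patient self-assessments "at seven time points (week 0, 8, 16, 24, 32, 40 and 52) in the study", and Table 1 agrees. Of those weeks, item f says: "These are times at which clinical care visits will routinely occur".

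Two self-report sources are described in enough detail to compare with the limits. The BISS-Self "is a 27item scale covering similar symptoms to the BISS, but answered as yes/no, rather than the 0-4 range of the BISS". The weekly KIOS-Bipolar questions are set out in Table 2, "BISS Item and Corresponding KIOS-BIPOLAR Questionnaire", which has eight rows. The eMoods items are not listed.

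**The concern.** This is a participant-protection rule, and staff need to be able to apply it from the page. A coordinator holding one mania score of 35 or more must end participation under Protections Against Risk and must not yet do so under Early termination. If the coordinator follows Early termination, the plan gives no means of finding out whether the four weeks have been met.

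The plan itself expects changes between visits: section c, Potential Risks, says "it is possible that a subject could worsen in a time frame between clinic treatment visits". The rule also bears on the analysis. Hypothesis a compares time in remitted and syndromal states, and these limits stop follow-up because of those states.

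**Working it through.** **1. The plan's one figure that touches the rule.** The Plan of analysis allows 30 of 120 subjects to meet an early-termination criterion: 120 − 30 = 90, and 30/120 = 25%. It claims 0.80 power for 0.65 against 0.5 at n = 90, two-sided 0.05.

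- Normal approximation: Φ[(0.15 × √90 − 1.96 × 0.5) / √(0.65 × 0.35)] = Φ[(1.423 − 0.980) / 0.477] = Φ(0.93) = 0.82.
- Exact binomial, upper rejection at 55 or more of 90: 0.81.

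The stated figure is reproduced. It does not depend on which wording applies.

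**2. The two statements, limb by limb.**

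| Limb | Early termination | Protections Against Risk | Conflict |
|---|---|---|---|
| Mania ≥ 35 | four-week duration on either reading | no duration | certain |
| Depression ≥ 50 | duration only if it governs the whole list | no duration | depends on reading |
| Suicide item = 4 | duration only if it governs the whole list | no duration | depends on reading |
| Psychiatrist's judgement of self-harm risk | no duration | no duration | none |

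One limb of four conflicts on the narrow reading, and three of four on the broad one.

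**3. Can scheduled ratings show four weeks?** Inputs: BISS-42 weeks 0, 8, 16, 24, 32, 40, 52 (item f and Table 1).

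- Gaps: 8 − 0 = 8, 16 − 8 = 8, 24 − 16 = 8, 32 − 24 = 8, 40 − 32 = 8, 52 − 40 = 12.
- The smallest gap is 8, which exceeds 4, so any four-week window holds at most one scheduled rating.
- Showing that a score has lasted four weeks needs at least a rating at each end. The schedule never supplies the second.
- Two successive high scheduled ratings would not prove continuous elevation. They would also come 8 weeks apart, or 12 if the first is at week 40, when the second falls at the end of the study.

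**4. Could another planned tool fill the gap?**

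- BISS-Self: yes/no items, so it cannot give an item score of 4 or a subscale total on the clinician scale. It is scheduled at the same seven weeks; Table 1 marks one further column, RS, which it does not define.
- KIOS-Bipolar: weekly, but only eight symptoms, none on suicide, and no BISS subscale total is described.
- eMoods: nothing in the documents says it yields BISS scores.
- Repeat or unscheduled BISS-42: not forbidden, but not called for anywhere.

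**The case against.** The strongest reply is that Early termination is the dedicated section, so it governs, and Protections Against Risk merely abbreviates it. That is plausible, but the documents do not say so. It would also leave in force the version that cannot be carried out on the schedule.

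A second reply is that sites can order extra ratings and will act alike, because the sponsor supplies an "identical set of study binders containing source documents and case report forms for each of the study sites" and monitors compliance. This makes divergence between sites less likely. It does not tell anyone which wording the forms should carry, or when a confirming rating is due.

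A third reply is that little harm follows. The psychiatrist clause is the same in both places. Section c undertakes to pass evidence of worsening to the treating clinician, although item g says no data go to treating clinical staff, so the route is unclear. The protocol describes the study as having no intervention component, and routine care continues. So termination ends app entries and ratings, not treatment. All of this stands and limits the consequence.

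Three stronger readings are tempting, and the documents do not support them:

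- **A suicide item score of 4 must persist for four weeks.** A reader might infer this, but the sentence can equally be read as attaching the duration to mania alone.
- **Participants are left unprotected.** The psychiatrist clause and continuing care say otherwise. Correcting the wording would not detect worsening between visits either, because the ratings stay 8 or 12 weeks apart.
- **The duration is an error and must be deleted.** Whether one high mania rating or a sustained elevation should end participation is a clinical decision.

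**Conclusion.** The point holds as an internal inconsistency together with a duration that cannot be established as planned. The inconsistency is certain for Mania of 35 or more. It extends to Depression of 50 or more and to the suicide item only on the broad reading of the sentence. The feasibility finding rests on the stated schedule and on the absence of any planned repeat rating; unscheduled ratings could overcome it, but the plan does not provide for them.

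Its practical size is unknown, because the documents give no rate at which subjects exceed the limits. A reader might infer that the allowance of 30 early terminations is therefore wrong. The documents give no basis for that either way. The change is worth making because the rule protects participants and the correction is cheap.

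**What to change.** Put one identical rule in Early termination and in Protections Against Risk, workable on the scheduled visits:

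1. A suicide item score of 4 at any BISS-42 rating ends participation, with no duration.
2. For Mania of 35 or more, and for Depression of 50 or more if the duration was meant to cover it, the clinical team chooses one of two forms:
   - **Single rating:** the limit applies at one scheduled BISS-42, as Protections Against Risk already has it.
   - **Sustained elevation:** keep the duration and state how it is confirmed, for example by a repeat BISS-42 four weeks after the first high score, with a second score over the limit counting as sustained.
3. Leave the psychiatrist clause as it is.

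The single-rating form needs only wording and no new data. It would end somewhat more participation early, and those stops are triggered by the mood states that Hypothesis a compares, so more follow-up would be cut short because of the outcome. The sustained form loses less follow-up but costs an occasional extra clinician rating outside the routine visit weeks. Neither changes the sample size or power.

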**C. Hypotheses:**

a. Patients randomized to KIOS- Bipolar compared with those randomized to eMoods will have a higher proportion of time in remitted status, lower proportion in syndromal status (Manic, depressed, mixed) and higher

LFQ scores.

- b. Persistence with use of KIOS- Bipolar and eMoods will not differ. Persistence is defined as 1) the proportion of subjects who complete weekly scheduled use of the bipolar self-assessment scales and 2) completion of the 52 week self-assessment protocol.
- c. The proportion of on-time completion of assessments will not differ between groups.
- d. Subject satisfaction, assessed by qualitative questionnaires completed by subjects during and principally shortly following completion or discontinuation of the trial, will not differ between groups.
- e. LFQ subscales will be associated with superior outcomes for the KIOS-Bipolar group.
- f. Correlations between scores on items included in KIOS- Bipolar and similar items on the BISS SR and the BISS 42 will be conducted. Strength of association will be higher between KIOS- Bipolar and BISS comparisons than eMoods-BISS comparisons.
- g. Aggregate changes for the KIOS- Bipolar items and corresponding eMoods items will indicate greater proportions of decreased scores for KIOS- Bipolar

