#### **ASSESS KIOS-BIPOLAR OR eMOODS:**

- a. At the beginning of the study subjects will be provided preformatted evaluation sheets and will be encouraged to note observations regarding ease/benefits of use, impediments to use, and suggestions for additional features that would enhance the utility of KIOS-Bipolar or eMoods for sustained health.
- b. We will ask the subjects to estimate how completing the KIOS-Bipolar /eMoods assessments contributed to their self-awareness, attitude, and overall sense of satisfaction with their health status.
- c. We will assess the sensitivity of KIOS-Bipolar to identify improving or worsening by comparing the concordance between subject-assessed items with staff -administered BISS items that address similar symptoms.

**Plan of analysis:** The primary aims of the analyses are to investigate patterns of adherence and attrition. The term adherence refers to the extent to which participants follow the weekly completion of KIOS-Bipolar's eight pivotal symptoms of bipolar disorder. Adherence will be measured through such usage indicators as the proportion of weeks completed on time, the proportion completed only with follow-up prompts, and the number of weeks not submitted. Proportions of stable trajectories or improving trajectories are of primary interest. With  $n=90$  subjects (which allows for as many as 30 of the enrolled 120 subjects to have met some criterion for early termination) in the study we will be able to estimate any proportion within 0.10 with 95% confidence. For proportions larger than 0.9 we will be 95% confident we are within 0.06 of the true proportion. For a trajectory neither improving nor degrading there should be a 0.5 proportion

UTHSCSA tracking number: HSC20150321H

of each. For any hypothesis test for a proportion improving or degrading, i.e. not 0.5, we have 0.80 power at two tail significance of 0.05 to detect 0.65 different from 0.5 with n=90 subjects. For subgroups of patients with n=45 we can detect 0.71 different from 0.5 and with n=30 we can detect 0.74 different from 0.5. When comparing proportions of two subgroups of subjects, we will be 95% confident that the difference in proportions of the two subgroups is less than 0.25 for subgroups of n=30 and smaller than 0.20 for subgroups of size 40. If the proportions are larger than 0.9 (i.e. less variable), then we will be 95% confident that the difference in proportions of two subgroups with n=30(45) is less than 0.15 (0.12).

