Assumptions needed for each analysis will be examined to assure they are reasonably well met and the conclusions are valid. End of study overall improvement or not for each measure can be analyzed with logistic regression using covariates and predictors of interest. By focusing analyses on proportions and changes in trajectories, each subject will serve as their own control and trends in improved scores, symptoms and behavior may be identified.

Initially, we will also assess the effects of site, ethnicity, and bipolar disorder subtype (BD I, BD II), but none of these factors will be retained in the final model if they are not shown to be significant moderating factors.

The rate of dropout at any given time will be modeled through logistic regression models, with health, socioeconomic, and treatment factors as explanatory variables. *The impact of quality of life on dropout will be assessed similarly.*

**Outcome Measures from KIOS Analytics:** Knowledge Base performance metrics will be computed to measure the effectiveness of the content provided to patients. These metrics take several forms and are based on changes in the symptom scores for all subjects in the field trial (see Phase I Final Report). Changes in the symptom scores provide a global measure of efficacy. Each of these measures can be computed as a function of changes, either over the course of the entire field trial or at each incremental assessment. This latter approach will provide a measure of effectiveness over time. Other KIOS analytic methods will reveal which specific content in the knowledge base needs improvement. Behavioral frequency analysis will show which patient states are entered most frequently. Behavioral transition analysis will show which conditions are precedents to undesirable states.

**Implementation of Clinical Trial Results into Final Product:** The results of the randomized trial will be used to make further refinements to KIOS-Bipolar. The KIOS-generated results will be used to guide changes to the knowledge base. Suggestions about additional features will be considered in development of the commercialization plans.

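### Hypothesis g measures each arm with its own app, so a between-arm difference in decreased scores cannot on its own be attributed to the assigned app

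*Combined protocol and SAP*

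**What the plan says.** Section C, Hypothesis g: "Aggregate changes for the KIOS- Bipolar items and corresponding eMoods items will indicate greater proportions of decreased scores for KIOS- Bipolar". This sets KIOS-Bipolar items in one arm against eMoods items in the other.

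The item map in Table 2 pairs eight BISS items with KIOS-Bipolar questions and has no eMoods column. Section D leaves the final KIOS-Bipolar input design to Aim 1.1. The only response formats stated belong to the BISS scales: BISS-Self is "answered as yes/no, rather than the 0-4 range of the BISS". The text below Table 1 limits the BISS comparisons to symptom areas "represented in both K-B and eMoods, e.g., depression and mania subscales; depression, mania, irritability and anxiety domains".

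The plan of analysis says: "Proportions of stable trajectories or improving trajectories are of primary interest". It gives a benchmark, "For a trajectory neither improving nor degrading there should be a 0.5 proportion", and an argument for looking at change: "By focusing analyses on proportions and changes in trajectories, each subject will serve as their own control". The Phase I result in the Abstract is put in similar terms: "patients had significantly more reductions in symptom severity than increases".

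BISS-42 and BISS-Self are scheduled in both arms (Table 1 and objective f): "at seven time points (week 0, 8, 16, 24, 32, 40 and 52) in the study".

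**The concern.** The proportion of scores that fall depends on the patient and also on the tool: what the items ask, how many response levels they have, and how reliably they register change. In g the tool changes with the arm. Two groups of patients with identical courses could therefore show different proportions of decreases.

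The own-control argument does not remove this. Subtracting a baseline takes out differences in score level, but not differences in item content, granularity or sensitivity to change. The plan also gives a reason to expect unequal tools: Hypothesis f predicts that KIOS-Bipolar will be more strongly associated with BISS than eMoods will. Participants who switch apps for technical reasons, as the Software section allows, would in addition have scores from two tools.

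At stake is whether a favourable result in g could be presented as evidence that KIOS-Bipolar reduces symptoms more than eMoods does.

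**Working it through.** **1. The plan's own figures.** None is stated for g. The nearest is 0.80 power to detect 0.65 against 0.5 with n = 90, two-sided 0.05. An exact binomial calculation gives 0.812, so it reproduces. The precision figure also reproduces: 1.96 × √(0.5 × 0.5/90) = 0.103. Both are one-sample figures and do not cover a comparison of arms.

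**2. What is specified for g.**

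| Needed for a like-for-like comparison | In the documents |
|---|---|
| KIOS-Bipolar items | Yes, Table 2 |
| eMoods items | No |
| KIOS-Bipolar response scale | No; input design left to Aim 1.1 |
| eMoods response scale | No |
| Linking rule | No; shared areas are named for the BISS comparisons only, as examples |
| Whether unchanged scores count | Not stated for g |

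On the last row, the 0.5 benchmark and the Phase I summary fit leaving unchanged scores out. However, the plan of analysis does not name g and also counts stable trajectories, so the question stays open.

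**3. Illustration of the mechanism.** Every input here is an assumption. Patients are identical in both arms. Baseline and follow-up severity are bivariate normal with SD 1, correlation r and mean fall δ. Scores are cut into K levels equally filled at baseline, at Φ⁻¹(j/K). With lo(x) and hi(x) the bounds of the level containing x:

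- P(decrease) = ∫ φ(x) Φ[(lo(x) − rx + δ)/√(1 − r²)] dx
- P(increase) = ∫ φ(x) {1 − Φ[(hi(x) − rx + δ)/√(1 − r²)]} dx

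*Number of levels* (r = 0.3, 0.5, 0.7):

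| K | Unchanged included, δ = 0: P(decrease) | Unchanged excluded, δ = 0.2: decreases/(decreases + increases) |
|---|---|---|
| 4 | 0.338, 0.306, 0.261 | 0.585, 0.603, 0.637 |
| 5 | 0.368, 0.340, 0.298 | 0.582, 0.599, 0.632 |
| 11 | 0.438, 0.421, 0.395 | 0.574, 0.590, 0.618 |

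With unchanged scores excluded and δ = 0, the proportion is 0.500 for every K and r, so the artefact is 0. With a common fall of 0.2 SD it is 0.3 to 0.5 points (4 against 5 levels) and 0.7 to 1.4 points (5 against 11). With unchanged scores included and δ = 0 it is 3.0 to 3.7 points (4 against 5) and 7.0 to 9.7 points (5 against 11).

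*Sensitivity to change* (K = 5 in both arms, true fall 0.2 SD, reliability 0.6 against 0.8). Observed correlation = true correlation × reliability; observed fall = 0.2 × √reliability.

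| True correlation | Unchanged excluded | Unchanged included |
|---|---|---|
| 0.5 | 0.564 v 0.580 (+1.7 points) | 0.416 v 0.413 (−0.3) |
| 0.7 | 0.571 v 0.596 (+2.5) | 0.403 v 0.394 (−0.9) |
| 0.8 | 0.576 v 0.607 (+3.2) | 0.396 v 0.382 (−1.3) |

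A plus sign favours the more reliable tool. The denominator rule changes the sign, although the negative gaps are small.

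**4. Scale against sampling error.** Assume 1:1 allocation (the ratio is not stated), one binary outcome per person, and 90/2 = 45 per arm. The 95% half-width for a difference near 0.5 is 1.96 × √(2 × 0.25/45) = 0.207. An artefact of 3.2 points raises the two-sided rejection rate from 5% to about 6%. A separate simulation used unequally filled levels, reliability 0.8, correlation 0.6, no true change and unchanged scores included. It gave 0.292, 0.343 and 0.424 for 4, 5 and 11 levels. The chance of a significant difference in the direction of the artefact was then 7% (4 against 5) and 25% (4 against 11).

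**The case against.** The strongest reply is that the artefact may be small. On the reading closer to the 0.5 benchmark it is at most 3.2 points in these illustrations, against a half-width of about 21 points. The larger values need the other denominator and a contrast of 5 against 11 levels for which the documents give no basis. This stands as a limit on size. It does not remove the confounding: g does not state the favourable denominator, and aggregating weeks or items would narrow the interval and leave the artefact in place.

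Three stronger readings are tempting but not supported.

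- A reader might infer that the two apps differ in wording, levels and sensitivity. The documents are silent on this; silence shows that comparability is undemonstrated, not that the tools differ in each respect.
- A reader might infer that g is uninterpretable in either direction. The figures above do not show that.
- A reader might infer either that Hypothesis a is free of the problem or that it shares it. The documents do not say which instrument defines the clinical states, and the heading of section D names both BISS and K-B.

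It is also fair to say that naming shared symptom areas, and relating each app to BISS in Hypothesis f, goes part of the way. Neither supplies a linking rule for g.

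**Conclusion.** The point holds in a bounded form. Arm and instrument coincide in g, and nothing in the documents establishes that the two app scores are comparable, so a between-arm difference in g cannot on its own be attributed to the assigned app. The size of any bias is unknown; the ranges in the working rest entirely on assumed scales, correlations and reliabilities and show only the mechanism.

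The consequence is limited. Hypothesis g is the last of seven, and LFQ, used in Hypotheses a and e, is common to both arms. It is still worth correcting, because improving trajectories are described as being of primary interest, although that sentence does not refer to g by name. Whether the time-in-state part of Hypothesis a is affected depends on an instrument that the documents do not identify.

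**What to change.** Make the between-arm test in g on an instrument common to both arms: the BISS-42 subscales and domains that the text below Table 1 names as shared by both apps. Use BISS-Self as the self-report companion, because the study is open and no masking of the clinician raters is described. Do not use all eight Table 2 items, since KIOS-Bipolar was derived from them. Define a decrease, and state whether unchanged scores count in the denominator. Report app-score changes within arm as description only, listing items and response scales for both apps. State which instrument defines the clinical states in Hypothesis a.

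The cost is protocol and analysis wording; no visit or form is added. The downsides are:

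- seven time points in place of weekly data;
- a shift of g from app self-report to clinician rating, with possible unblinded-rater bias;
- a coarse yes/no BISS-Self;
- some remaining overlap between the BISS domains and the KIOS-derived items (sadness, irritability and anxiousness are in Table 2);
- eMoods coverage of the named areas, which are given as examples, still to be confirmed by the sponsor.
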